Endpoints	
Primary Efficacy Endpoint: Recurrence of CDI within 8 weeks of blinded treatment.
 
Secondary Efficacy Endpoint: Loss of sustained clinical response through 6 months after blinded treatment.
 
Safety Endpoints:
 
1. Number of adverse events per subject2. Timing of attributable adverse event post-treatment exposure (treatment emergent adverse event TEAE)3. Duration of TEAE4. Relatedness of TEAE5. Severity of TEAE6. Causality of TEAE to IP, enema, C difficile or prior condition7. Number of each of the following through 8 weeks post blinded treatment: death, septic shock, toxic megacolon, colonic perforation, emergency colectomy, and ICU admission.8. Onset of new chronic conditions relative to blinded treatment administration
Study Design	
This is a prospective, multicenter, randomized, double-blinded, placebo-controlled Phase 3 study to confirm the efficacy and safety of RBX2660 for the prevention of recurrent CDI.
 
Up to 270 subjects may be randomized and treated in this study. Randomization will be at a 2:1 ratio (RBX2660:Placebo); approximately 180 subjects will be randomized to RBX2660 treatment and 90 subjects randomized to Placebo. Consented subjects who meet all eligibility criteria (inclusion and exclusion) will be randomized. Consented subjects who do not meet the eligibility criteria will be considered screen failures and will not count towards the total randomized. Subjects who are randomized but exit prior to the administration of the first blinded enema may be replaced with additional subjects which could cause overall number of subjects randomized to be greater than the 270 anticipated, however no more than 270 subjects will be treated with a blinded enema. Any replacement subjects will be randomized to ensure maintenance of proper blinding.
 
Potential subjects are expected to already be taking or have just been prescribed antibiotics to control recurrent CDI symptoms at the time of enrollment per the investigator's standard of care. This means patients who have already completed their prescribed course of antibiotics to treat

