	
recurrent CDI, are not eligible for enrollment unless they have another recurrence that is treated with antibiotics.
 
Once enrolled (informed consent obtained), in order to be randomized and treated:
 
1. Subject must meet all the inclusion and none of the exclusion criteria;2. Antibiotics will have been administered for a minimum of 10 consecutive days prior to the washout period;3. CDI symptoms must be under control leading into the antibiotic washout period. 
Control of CDI symptoms is defined as no longer meeting the symptomatic criteria for CDI diarrhea which is the passage of three or more unformed/loose (i.e. Bristol Stool Scale type 6-7) stools in 24 or fewer consecutive hours for at least two consecutive days while taking antibiotics. Thus, at minimum the Subject Diary (completed from time of enrollment until day of treatment) must show that symptoms are under control the two days prior to the washout period in order for the subject to be treated.
 
Once screening is completed and all inclusion and exclusion verified, the subject can be randomized. The assigned study treatment will be scheduled to consist of a single, blinded study enema according to the randomization assignment. Study treatment is to be completed as soon as possible, but no more than 14 calendar days following randomization. Ultimately, the study treatment needs to be administered within 21 days of the Screening visit. A minimum of 24hr to maximum of 72hr antibiotic washout period is required prior to administration of the assigned study treatment.
 
In-office study follow-up visits occur at weeks 1, 4 and 8 after completing the blinded study treatment. Telephone assessments for adverse events occur during weeks 2, 3 and 6 after the study enema and at months 3 and 6. Subjects are required to keep a detailed diary to assess for solicited events from the date of enrollment (informed consent) to the 1-week follow-up visit. The diary will be collected and reviewed at the baseline visit prior to blinded enema administration. The subject will continue to complete the diary following enema administration and it will be collected and reviewed at the 1-week follow-up visit.
 
Subjects who are deemed failures following the blinded treatment per the pre-specified treatment failure definition may elect to receive an unblinded RBX2660 enema. This unblinded enema is to be administered within 21 calendar days of failure determination. If a subject receives an

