5.4. Treatment Regimen

Randomization is to occur about 4-14 calendar days prior to the blinded study treatment to allow for notification to Rebiotix and shipment of product. Ultimately, the study treatment needs to be administered within 21 days of the Screening visit. Subjects are randomized to one of the following groups:

- Group A: Placebo
- Group B: RBX2660

Randomization will occur in a 2:1 fashion with two subjects randomized to receive RBX2660 for every one subject randomized to Placebo.

Once completed, assigned study treatment consists of a single blinded enema of either RBX2660 or Placebo as per the randomization assignment. Product is to only be administered by the authorized IP Administrator who must be a qualified and trained health care professional following the Instructions for Use and standard site procedures. Subjects are to remain at the site under supervision for at least one hour post-enema administration for vital sign assessment (temperature, heart rate, blood pressure, respiratory rate) and observation.

Subjects with a documented treatment failure following blinded treatment may be scheduled for administration of an unblinded RBX2660 enema. In order to receive an unblinded RBX2660 enema, a subject must have documentation of meeting all treatment failure criteria as defined by the protocol (Section 3.7).

If, in the opinion of the investigator, antibiotics are warranted for the control of CDI symptoms prior to receiving the unblinded RBX2660 enema, they can be administered but need to be stopped 24-72 hours before enema administration. The total time from a treatment failure (CDI recurrence) determination to administration of an unblinded enema is within 21 calendar days.

See Section 6 for the Schedule of Study Procedures and detailed description of the requirements.

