6.5. Screening Visit

The following study activities/data will be collected at the screening visit:

- Subjects are told about the study and informed consent is obtained (enrollment)
- Standard demographics (gender, ethnicity, date of birth, race.)
- Detailed medical history, including Charlson Comorbidity Index variables
- Assess inclusion/exclusion criteria, including *C. difficile* stool testing
 - At the time of enrollment or study entry, a positive stool test for toxigenic *C. difficile* must be or have been performed and documented no more than 30 days before entry and must be on file at the site. *C. difficile* laboratory testing according to the site's standard of care is acceptable for enrollment, however, the use the C. DIFF QUIK CHEK COMPLETE® Test rapid enzyme immunoassay test for enrollment is preferred. If the rapid enzyme immunoassay test is utilized, the same interpretation of results as defined for treatment failures is required.
- Core laboratory blood sample is collected for CBC w/differential and comprehensive metabolic panel (CMP: Sodium, potassium, chloride, BUN, creatinine, albumin, AST, ALT, alkaline phosphatase, bilirubin (direct, indirect and total), glucose) and C-reactive protein (CRP) testing
- Onsite urine pregnancy test for subjects of child bearing potential
- For subjects who consented to the Optional Stool Sample collection, remind them to obtain and ship a stool sample to Rebiotix anytime between their enrollment date and their blinded enema administration visit
- Assess vital signs: height, weight, temperature, blood pressure, pulse, respiration.
- Complete the Cdiff32 health-related quality of life questionnaire

- Document concomitant medications
- Completion of the Subject Diary is explained and how to complete it is demonstrated; see Section 6.3.
- Verify employment status
- Assess for protocol deviations

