6.2 Time Point Algorithms

6.2.1 Relative Day

The date of study enema administration will be considered relative day 1, and the day before study enema administration will be relative day -1. Relative days will be calculated as follows only when the full assessment date is known (i.e., partial dates will have missing relative days, unless imputation methods have been specified):

For days before first enema:

Date of Assessment – Date of first enema administration

For days on or after first enema:

Date of Assessment – Date of first enema administration +1

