6.2.2 Windows

For the purpose of statistical analysis, the analysis visit windows will be calculated in terms of study days since the day of the study enema administration, as illustrated in the following tables:

Analysis Windows for Clinical Visits

Visit	Scheduled Study Day	Visit Window in Protocol (Days)	Visit Window for Analysis (Days)
Screening Visit	-30 through -1	-30 through -1	-30 through -10
Baseline/1 st Enema	1	1	1
Week 1 Office	8	5 - 11	5 - 11
Week 4 Office	29	26 - 32	26 - 32
Week 8 Office	57	54 - 60	54 - 60

Analysis Windows for Phone Assessments

Visit	Scheduled Study Day	Visit Window in Protocol (Days)	Visit Window for Analysis (Days)
Week 2 - Phone	15	12 - 18	12 - 18
Week 3 - Phone	22	19 - 25	19 - 25
Week 6 - Phone	43	40 - 46	40 - 46
3 month - Phone	90	76 - 104	76 - 104
6 month - Phone	180	166 - 194	166 - 194

If a subject has more than one assessment occurring in the same visit window, the data from the visit closest to the scheduled study day will be used for analysis. If two visits have the same distance from the scheduled study day, i.e., one visit occurs -1 day from study day, and the other visit occurs +1 day from study day, the data from the visit after the scheduled study day will be used for analysis.

Analysis Windows for Adverse Event Reporting by Onset Interval

Onset Interval Name	Onset Interval Analysis Window	Window for Analysis (Days)
Baseline	Screening - < Baseline	≤ -1
1-week	Baseline - 1-week	1 through 8
4-week	> 1-week - 4-week	9 through 29
8-week	> 4-week - 8-week	30 through 57
4-month	> 8-week - 4-month	58 through 121
6-month	> 4-month - 6-month	122 through 180+

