7.6.3 Other Endpoint Analysis

An initial assessment will be completed during the primary efficacy analysis as follow-up data allows with a complete analysis to be provided with the full study results for applicable other analyses. Additionally, the other analyses will be conducted on other efficacy populations as needed.

7.6.3.1 Comparison of baseline characteristics in subjects successful with one dose of RBX2660 vs. those who were unsuccessful.

A multivariate analysis or regression analysis will be used to identify predictors (if any) for subject success with one RBX2660 dose vs. those who were unsuccessful.

7.6.3.2 Cdiff32 scores at Screening, 1-week, 4-week, and 8-week assessment visits, and 3 and 6 month phone assessments.

Changes from Screening in the Cdiff32 scores will be summarized using descriptive statistics by treatment arm. Last observation carried forward (LOCF) will be used to impute missing post-baseline data. No inferential statistics will be performed.

7.6.3.3 Subject fecal microbial composition at Screening, and 4 and 8- weeks and 3 and 6 months after blinded study treatment.

Descriptive statistics will be used to present the changes from Screening fecal microbial composition to those at 4 weeks, 8 weeks, 3 months and 6 months after blinded study treatment for those subjects treated with RBX2660 and those receiving Placebo.

7.6.3.4 Charlson Comorbidity Index at Screening, 8 week visit, and 3-, 6- month phone assessments.

A comorbidity index score will be documented for all subjects at Screening and compared to subsequent scores at 8 weeks, 3 months and 6 months. An initial assessment will be completed during the primary efficacy analysis as follow-up data allows with a complete analysis to be provided with the full study results. Additional analysis may be done of Placebo subjects who

were documented treatment failures after blinded treatment then treatment successes following unblinded RBX2660 treatment.

7.6.3.5 Atlas score for CDI severity of qualifying CDI.

Quantification of CDI severity scores for subjects at the time of the CDI recurrence that qualified them for enrollment into the study based on the ATLAS Scoring System. Data from the qualifying CDI event will be used (see table below), including the protocol required eligibility criteria of treatment with systemic antibiotics prior to randomization. However, if data points are not available, baseline data may be substituted.

Parameter	0 Points	1 Point	2 Points

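### The SAP's Screening analysis window ends at day -10, in conflict with its own protocol column, SAP 7.3 and the protocol's timing rules; read literally, it leaves some valid Screening values unassigned

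*Protocol*

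**What the plan says.** SAP 6.2.2 states that "the analysis visit windows will be calculated in terms of study days since the day of the study enema administration". In its table of clinical visits, the Screening row shows -30 to -1 as the protocol window and -30 to -10 as the analysis window. The only selection rule begins "If a subject has more than one assessment occurring in the same visit window"; nothing covers an assessment that falls in no window. SAP 7.3 places baseline assessments within 30 days before treatment or on the treatment day itself, with no cut-off at day -10.

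The protocol's timing rules are these:

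- Synopsis, Study Design (also 3.2, 5.4 and 6.6): "Ultimately, the study treatment needs to be administered within 21 days of the Screening visit". No minimum interval is given.
- 5.4: "Randomization is to occur about 4-14 calendar days prior to the blinded study treatment". Footnote 5 of the SAP 6.1 schedule repeats the 4-14 days.
- Synopsis, Study Design: "Potential subjects are expected to already be taking or have just been prescribed antibiotics". At least 10 consecutive antibiotic days must precede a 24-72 hour washout, and the diary must show control on the two days before the washout.
- 6.5: the optional Screening stool sample may be collected and shipped "anytime between their enrollment date and their blinded enema administration visit".

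Screening is the reference in SAP 7.6.3.2 ("Changes from Screening in the Cdiff32 scores will be summarized"), in 7.6.3.3 for fecal microbial composition and in 7.6.3.4 for the Charlson index.

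**The concern.** A subject who has already taken part of the antibiotic course can be screened fewer than 10 days before the enema in full compliance with the protocol. If the programmer follows the SAP 6.2.2 table, that Screening record belongs to no analysis visit, and the subject has no reference value.

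For two of the three analyses nothing else is scheduled to take its place. In the schedules of both documents, Cdiff32 and the medical history assessment are collected at Screening and not at the baseline/enema visit. Last observation carried forward in SAP 7.6.3.2 fills post-baseline values only, and SAP 8.3 allows no other imputation.

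At stake are the number of subjects in these summaries and whom they describe. The exposed subjects are some of those who had started antibiotics before Screening, so the loss would not be a random sample. The SAP also leaves the programmer to choose between 6.2.2 and 7.3, possibly after seeing data.

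**Working it through.** **Step 1. Rebuild the SAP window tables.** Inputs are the scheduled study days in SAP 6.2.2 and the tolerances in the schedule of events (3 days for office visits and weekly calls, 14 days for the month 3 and month 6 calls). Window = scheduled day ± tolerance.

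- Office visits: 8 ± 3 = 5-11; 29 ± 3 = 26-32; 57 ± 3 = 54-60.
- Weekly calls: 15 ± 3 = 12-18; 22 ± 3 = 19-25; 43 ± 3 = 40-46.
- Month calls: 90 ± 14 = 76-104; 180 ± 14 = 166-194.

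All eight post-baseline rows reproduce exactly, and in each the protocol and analysis columns are identical. Screening is the only row where they differ, and the SAP gives no reason for it.

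**Step 2. Find the latest allowed screening day.** SAP 6.2.1 sets the convention: "the day before study enema administration will be relative day -1". Screening *k* days before the enema is therefore day -*k*. The constraints are:

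- *k* ≤ 21 (maximum interval).
- *k* ≥ 4 + *L*, where 4 is the shortest interval from randomization to enema and *L* is the time needed for central laboratory confirmation before randomization (Protocol 6.6). The documents do not give *L*; I assume 0 to 3 days.
- *k* ≥ *w* + 2, for washout *w* of 1 to 3 days plus two diary days. At *w* = 1 this is *k* ≥ 3, which does not bind.
- Antibiotic days needed before Screening = max(0, 10 - (*k* - *w*)).

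With *w* = 1, the last formula gives 2 prior antibiotic days for screening on day -9, 3 on day -8, 4 on day -7, 5 on day -6, 6 on day -5 and 7 on day -4. A subject who starts antibiotics at Screening needs *k* ≥ 11 and is always inside the SAP window.

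**Step 3. Compare with the analysis window.**

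| Assumed *L* | Allowed screening days | Count | Later than day -10 | Share of allowed days |
|---|---|---|---|---|
| 0 | -21 to -4 | 18 | -9 to -4 (6 days) | 6/18 = 33% |
| 1 | -21 to -5 | 17 | -9 to -5 (5 days) | 5/17 = 29% |
| 2 | -21 to -6 | 16 | -9 to -6 (4 days) | 4/16 = 25% |
| 3 | -21 to -7 | 15 | -9 to -7 (3 days) | 3/15 = 20% |

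These are shares of calendar days, not of subjects.

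**Step 4. Screening stool.** Collection may take place on any day up to the enema visit. Even for a subject screened on day -21, 9 of the 21 days from -21 to -1 fall after day -10 (9/21 = 43% of days). For a subject screened on day -9 or later, all of them do.

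**Step 5. The other end of the window.** The analysis window holds 21 days (-30 to -10). Nine of them (-30 to -22) lie beyond the protocol's 21-day limit, so the window fits the protocol at neither end.

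**The case against.** The best reply is that the SAP nowhere says an out-of-window value is discarded. SAP 6.2.2 only chooses among several records in one window, SAP 7.3 accepts baseline data up to the treatment day, and SAP 7.6.3.4 expects a Charlson score at Screening for every subject. A sensible programmer might use the value anyway. This stands as far as it goes: exclusion follows from a literal reading of the table and is not a stated rule. It does not remove the contradiction between 6.2.2 and 7.3.

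The reply is also right about reach. A reader might infer that every analysis referring to baseline is hit. The documents do not support that. The diary severity summaries have their own baseline (SAP 7.7.2.1), ATLAS allows baseline data to be substituted (7.6.3.5), and *C. difficile* presence is assessed for trends, with no stated change from Screening (7.6.3.10). Cdiff32 and microbial composition are descriptive only, the stool samples are optional, and no test is named for Charlson.

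A reader might also turn the 20% to 33% of days into a percentage of subjects, or into a loss of precision. That needs a distribution of screening-to-enema intervals, which neither document gives.

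Nor does the window fit only newly prescribed subjects. Someone with 4 antibiotic days completed could be treated 7 days after Screening at the earliest, but with 3 or more further days of scheduling is screened on day -10 or earlier and is inside the window. The stool exposure also assumes that a table for clinical visits governs samples shipped from home, which the SAP does not say.

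**Conclusion.** The inconsistency is real and should be corrected, but its reach is narrow. SAP 6.2.2 conflicts with its own protocol column, with SAP 7.3 and with the protocol's timing rules. Read literally, it leaves valid Screening values on days -9 to about -4 unassigned. That would affect the Cdiff32 and microbial composition summaries and the Charlson comparison, all of which belong to the other efficacy endpoints.

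The size is 20% to 33% of allowed screening days, on the assumption of 0 to 3 days' laboratory turnaround and with antibiotic days before Screening counting toward the 10. The number of subjects is unknown. The primary and secondary endpoints use no Screening value and are untouched. The documents give no reason to expect a bias between the arms: an early or late Screening depends on antibiotics begun before Screening and on scheduling before the blinded enema.

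**What to change.** In the SAP 6.2.2 table, change the Screening analysis window to -30 through -1, which agrees with the protocol column beside it and with SAP 7.3. Alternatively use -21 through -1, which matches the protocol's 21-day limit; in that case correct the protocol column as well.

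Add one sentence stating that the reference value for Cdiff32, Charlson and the Screening stool endpoints is the last non-missing value before the blinded enema. The sentence is needed as well as the table cell. A stool sample taken on the enema day before dosing is day 1 and would miss either window, and the closest-to-scheduled-day rule cannot work for Screening, whose scheduled day is itself a range.

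The cost is one table cell and one sentence (plus the protocol column under the alternative), with no new patients or data. It should be done before unblinding.
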